#### 5.6.1.1 Definition of binary endpoints

The primary endpoint (IGA CHE TS at Week 16) for LP0133-1426 will be the only endpoint analysed with the treatment policy strategy estimand.

#### 5.6.1.2 Analysis for the supplementary estimand

Observed data will be used in the analysis, including the data observed after the occurrence of IEs. To support the treatment policy strategy, subjects who experience IEs prior to Week 16 will be asked to attend the primary endpoint visit at Week 16 for collection of data.

Missing data at Week 16 will be imputed using MI (100 iterations) assuming MAR within treatment group. For further detail on the MI procedure see section 5.1.1.1. For each of the 100 imputed datasets, the risk difference will be based on a logistic regression model including treatment group and baseline IGA-CHE score as factors. The results of the analyses will be combined using Rubin’s rule to provide the estimated treatment difference and associated standard error, and the 95% CI for the treatment difference will be calculated. In case of no missing data this analysis will not be performed.

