## 14.3.5 Estimand strategy

### 14.3.5.1 Overview

The analysis of endpoints related to efficacy and health-related quality of life will be based on the full analysis set.

For the analyses based on the Bayesian approach, only the primary estimand using the composite strategy will be used.

For the analyses based on the Frequentist approach, both the primary estimand (using the composite strategy) and the supplementary estimand (using the treatment policy strategy) will be considered for the primary endpoint while only the primary estimand will be considered for the key secondary endpoints (remaining binary endpoints) and other continuous endpoints.

THIS DOCUMENT CONTAINS CONFIDENTIAL INFORMATION AND MUST NOT BE COPIED OR MADE AVAILABLE TO ANY THIRD PARTY WITHOUT THE PRIOR WRITTEN CONSENT OF THE LEO PHARMA GROUP

The primary estimand will use a composite strategy to handle IEs. With a composite strategy, the occurrence of an IE is a component of the endpoint.

A supplementary estimand will use a treatment policy strategy which attempts to quantify the effect of the randomised treatment, ignoring the occurrence of IEs. Data collected for the endpoint of interest are used regardless of whether an IE occurred.

For the composite and treatment policy estimands, prespecified sensitivity analyses will be conducted to assess the robustness of the results with respect to the handling of missing data. The pre-specified sensitivity analysis will only be performed for the primary endpoint as a low IMP discontinuation rate is anticipated in the relatively small sample size (69 subjects on delgocitinib cream vs. 23 subjects on cream vehicle) and the expected low amount of the missing data. These sensitivity analyses will only be performed for the analyses based on the Frequentist approach when mentioned.

In addition, sensitivity analyses of the influence of weight on the non-informative part of the prior will be made for the Bayesian approach, see Section [14.3.17](#).

The following IEs are considered to affect the interpretation of the estimated treatment effects:

- **Initiation of rescue treatment:** This IE occurs when a subject initiates rescue treatment. This IE can occur at the discretion of the investigator. If rescue treatment is initiated, the subject must stop treatment with IMP immediately and will not be allowed to restart treatment with IMP (refer to Section [9.5](#) for details).

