##### **Supplementary estimand: treatment policy strategy (used for the Frequentist approach)**

This supplementary estimand evaluates the treatment effect in adolescents 12-17 years of age with moderate to severe CHE, regardless of initiation of rescue treatment or permanent discontinuation of IMP.

Observed data will be used in the analysis, including the data observed after the occurrence of IEs. To support the treatment policy strategy, subjects who experience IEs prior to Week 16 will be asked to attend the primary endpoint visit at Week 16 for collection of data.

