## 5.1.1 Handling of missing values

### 5.1.1.1 Multiple imputation

#### 5.1.1.1.1 Multiple imputation based on missing at random assumption (MAR)

Multiple imputation will only be performed for the primary endpoint.

For the treatment policy estimands' analyses the MI method includes the use of the FCS method assuming MAR to impute missing data. When analyses require MI procedures of data, 100 complete datasets will be generated.

MI under the MAR assumption will be performed using PROC MI in SAS with the FCS method 'logistics' for arbitrary missing patterns (1). Section 7.2 provides an example of SAS code to perform MI.

When analyses require MI procedures of data, the multiple-imputed datasets will be created in the following way:

1. A dataset will be created with longitudinal data in wide format (one row per patient).
2. For each timepoint missing (weeks 2, 4, 8, 12 and 16) values will be imputed using PROC MI within treatment group for IGA-CHE. The regression model for a certain timepoint will include the 2 preceding and 2 subsequent timepoints as predictors, in addition to baseline IGA-CHE score. Exceptions being the first 2 and last 2 timepoints, where the number of previous and subsequent timepoints are reduced to zero or one.
3. IGA-CHE TS is derived based on the imputed score for each of the 100 datasets and will be derived from imputation of the underlying ordinal score.
4. The relevant model is fitted for the 100 complete datasets, and Rubin's rule is applied, in order to derive the estimated treatment difference, associated SE and CI.

If there are no between-imputation variance, i.e., all the 100 imputed datasets are identical, it will not be feasible to estimate the variance using Rubin's rule for MI. Instead, the first imputed dataset will be used for analysis.

For imputation of IGA-CHE scores, it may occur that the observed data from which the imputation model is fitted does not contain all categories of the IGA-CHE predictors necessary for the imputation. For example, if all subjects with an IGA-CHE score of 3 at Week 12 have missing data at Week 16, then a regression model based on Week 12 data cannot predict the Week 16 outcome in those subjects, unless the IGA-CHE score of 3 at Week 12 is combined with other IGA-CHE scores. To avoid this situation, in this example

THIS DOCUMENT CONTAINS CONFIDENTIAL INFORMATION AND MUST NOT BE COPIED OR MADE AVAILABLE TO ANY THIRD PARTY WITHOUT THE PRIOR WRITTEN CONSENT OF THE LEO PHARMA GROUP

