## 5.4 Estimand overview

The primary endpoint for LP0133-1426 is IGA-CHE TS at Week 16, and the primary estimand uses the composite strategy when handling intercurrent events. With a composite strategy, the occurrence of an IE is a component of the endpoint.

For the analyses based on the Bayesian approach, only the primary estimand using the composite strategy will be used.

For the analyses based on the Frequentist approach, both the primary estimand (using the composite strategy) and the supplementary estimand (using the treatment policy strategy) will be considered for the primary endpoint. For the other endpoints the primary estimand will be the only one used.

The supplementary estimand uses a treatment policy strategy which attempts to quantify the effect of the randomised treatment, ignoring the occurrence of IEs. Data collected for the endpoint of interest are used regardless of whether an IE occurred.

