### 5.5.1 Primary estimand for binary endpoints: composite strategy, used for both the Bayesian approach and the Frequentist approach

The primary estimand “Composite strategy” evaluates the treatment effect in adolescents 12-17 years of age with moderate to severe CHE as the risk difference for achieving a response, without initiation of rescue treatment or permanent discontinuation of IMP.

For subjects who received rescue treatment or who have permanently discontinued IMP prior to the endpoint of interest, observed data after the IEs will be considered non-response, reflecting an assumption that initiation of rescue treatment and permanent discontinuation of IMP indicate failure of the randomised treatment.

For example, the primary composite endpoint of IGA-CHE TS at Week 16 without initiation of rescue treatment or permanent discontinuation of IMP can take the values:

- ‘1’ (response), if the subject achieves IGA-CHE TS at Week 16 and has neither initiated rescue treatment nor permanently discontinued IMP prior to Week 16.

THIS DOCUMENT CONTAINS CONFIDENTIAL INFORMATION AND MUST NOT BE COPIED OR MADE AVAILABLE TO ANY THIRD PARTY WITHOUT THE PRIOR WRITTEN CONSENT OF THE LEO PHARMA GROUP

- '0' (non-response), if the subject has not achieved IGA-CHE TS at Week 16 or has initiated rescue treatment or permanently discontinued IMP prior to Week 16.

Missing data for subjects who do not experience an IE prior to the visit for the endpoint of interest will be imputed as non-response, except in the sensitivity analysis where these are imputed from a Bernoulli distribution. Similarly, missing data at the endpoint of interest for subjects who do experience an IE prior to this visit will be imputed as non-response.

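### The main treatment-policy analysis is cancelled when no Week 16 data are missing, although that is when the estimand is best estimated and it can still differ from the composite one

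*SAP*

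**What the plan says.** The supplementary estimand for IGA-CHE TS at Week 16 is treatment policy. SAP 5.4 defines it without reference to missingness: "Data collected for the endpoint of interest are used regardless of whether an IE occurred". Protocol 14.3.5.2 agrees: "Observed data will be used in the analysis, including the data observed after the occurrence of IEs". The primary, composite estimand does the opposite with the same values; under SAP 5.5.1, "observed data after the IEs will be considered non-response".

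SAP 5.6.1.2 gives the main analysis: MAR multiple imputation of missing Week 16 data within treatment group (100 datasets), a logistic model with treatment and baseline IGA-CHE, and pooling by Rubin's rule. It also says why post-event data will exist: "subjects who experience IEs prior to Week 16 will be asked to attend the primary endpoint visit at Week 16 for collection of data". It then closes with "In case of no missing data this analysis will not be performed". Protocol 14.3.6 has the same rule in the same place. SAP 5.6.1.3, the sensitivity analysis that sets missing values to non-response, repeats it.

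**The concern.** The rule reads as if the treatment-policy analysis existed only to handle missing data. In SAP 5.5.1.3, the Bernoulli imputation check on the composite estimand, that is true: with nothing to impute, the result equals the primary analysis and nothing is lost. In 5.6.1.2 the analysis answers a different question from the primary one, and having nothing to impute does not merge the two.

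Subjects who stop IMP are asked back at Week 16 to support this estimand. If that retrieval succeeds fully, the rule drops the analysis it was meant to feed. The sensitivity analysis in 5.6.1.3 drops out with it, leaving at most the additional CMH version in 5.6.1.4. The rule also creates an odd break: one missing value brings the full analysis, and none brings no analysis.

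**Working it through.** **1. Do the estimands coincide when nothing is missing?** SAP Panel 8 for the binary endpoint, rows for observed data:

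| Subject | Composite | Treatment policy |
|---|---|---|
| Rescue started, Week 16 observed | Non-response | As observed |
| IMP stopped, Week 16 observed | Non-response | As observed |
| No intercurrent event, Week 16 observed | As observed | As observed |

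The first two rows differ and involve no missing value. The estimates coincide only if no subject with an intercurrent event is a Week 16 responder.

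**2. Is there a technical obstacle to running the analysis on complete data?** No. SAP 5.1.1.1.1 already covers 100 identical imputed datasets, where Rubin's rule gives no between-imputation variance: "Instead, the first imputed dataset will be used for analysis". A complete dataset is that case, so the skip rule pulls against this instruction. It also conflicts with SAP Panel 1, which lists the supplementary estimand without any condition.

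**3. How often would the rule apply?** Protocol 14.3.5.1 refers to "the expected low amount of the missing data" but gives no rate. Assume that each of 92 subjects independently has probability m of a missing Week 16 IGA-CHE. Then P(analysis cancelled) = (1 − m)^92:

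| Assumed m | P(cancelled) |
|---|---|
| 0.5% | 0.995^92 = 63% |
| 1% | 0.99^92 = 40% |
| 2% | 0.98^92 = 16% |
| 5% | 0.95^92 = 1% |

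**4. How far apart can the two risk differences be on complete data?** Arm sizes are from Protocol 14.3.5.1: "69 subjects on delgocitinib cream vs. 23 subjects on cream vehicle". Let a and v be the numbers of subjects with an intercurrent event who respond at Week 16 on delgocitinib and vehicle. Then

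RD(treatment policy) − RD(composite) = a/69 − v/23.

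Each such responder moves the difference by 1/69 = 1.4 points (delgocitinib) or 1/23 = 4.3 points (vehicle). The average adult effect in Protocol Panel 21 is 15.9 points.

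For illustration, take the protocol's hypothetical example 1 (Panel 32) as the composite result: 22/69 − 3/23 = 31.9% − 13.0% = 18.8 points, which matches the printed difference. (The panel prints the vehicle rate as 13.3%; 3/23 is 13.0%.) The documents do not give a and v, so the values below are assumptions. The intervals are crude 95% Wald intervals without baseline adjustment.

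| a | v | Treatment-policy RD, points (95% CI) | Shift from composite, points |
|---|---|---|---|
| 0 | 0 | 18.8 (1.2 to 36.5) | 0 |
| 1 | 1 | 15.9 (−3.1 to 35.0) | −2.9 |
| 2 | 2 | 13.0 (−7.2 to 33.3) | −5.8 |
| 0 | 3 | 5.8 (−15.2 to 26.8) | −13.0 |
| 4 | 0 | 24.6 (6.7 to 42.5) | +5.8 |

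One post-event responder per arm is enough to move the crude lower limit from above zero to below it.

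**The case against.** The best counter-argument is that the estimand is still estimated. SAP 5.6.1.4 plans a CMH test and a Mantel-Haenszel risk difference under treatment policy, stratified by baseline IGA-CHE, with the same use of post-event data. Its skip sentence follows the sensitivity version, so the main CMH version is not clearly cancelled. That stands, and it limits the harm. But that analysis is labelled additional and is there for comparison with the adult trials. It is not the logistic risk difference specified for this estimand, and the scope of its own skip sentence is unclear.

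Second, the missing rates are assumed, and several routes to a missing Week 16 score exist: refusal of the visit (Protocol 10.1), loss to follow-up (10.4), and remote visits without investigator efficacy assessments (Appendix 7). The SAP was also written after blind data review, so the pooled amount of missing data may already have been known. All true; the probabilities are conditional and may not describe the actual trial.

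Third, a real difference needs both complete data and at least one post-event responder. Protocol 14.3.5.1 expects few IMP discontinuations, and rescue itself requires stopping IMP (Protocol 9.5), so conditions that favour complete data also tend to bring the estimands together. This too stands. The two probabilities should not be read as one expected loss. It does not justify the rule: if the results agree, reporting that agreement is itself the finding.

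Fourth, only the Bayesian composite analyses enter the testing hierarchy. That is correct, and it bounds the importance of the point.

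**Conclusion.** The concern holds. As written, the rule cancels the specified main analysis of the treatment-policy estimand in the one situation where it needs no MAR assumption, even though that estimand can still differ from the composite one. With complete data the two risk differences separate by 1.4 points per post-event responder on delgocitinib and 4.3 points per post-event responder on vehicle, and are equal if there are none. The chance that the rule applies runs from 63% to 1% for assumed missing rates of 0.5% to 5%, taking subjects as independent and reading the trigger as no missing Week 16 IGA-CHE.

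The consequence is confined to a supplementary frequentist analysis. No confirmatory claim, type I error rate or power figure depends on it. It should be corrected, but it does not threaten the primary conclusion.

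**What to change.** In SAP 5.6.1.2, and in the matching paragraph of Protocol 14.3.6 if the protocol is amended again, replace the skip sentence with: *If no Week 16 data are missing, the same model is fitted once to the observed data without imputation.*

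Leave the skip rule where it is harmless: the missing-data sensitivity analyses in SAP 5.5.1.3 and 5.6.1.3, their counterparts in Protocol 14.3.6, and the sensitivity part of SAP 5.6.1.4. In 5.6.1.4, say explicitly that the rule applies to the sensitivity version only.

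Protocol 14.3.15 allows such a change to be described and justified in the SAP, and SAP Section 6 already records one, so a protocol amendment is not strictly needed. The cost is one sentence plus that clarification, with no extra data. It should be settled before unblinding so that running the analysis is not a post hoc decision.

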#### 5.6.1.3 Sensitivity analysis of the supplementary estimand

Observed data will be used in the analysis, including the data observed after the occurrence of IEs. Missing data at Week 16 will be imputed as non-response.

The risk difference will be analysed as described above for the analysis of the supplementary estimand. In case of no missing data this analysis will not be performed.

#### 5.6.1.4 Additional analyses for the primary endpoint using the supplementary estimand and the sensitivity analysis of the supplementary estimand

To be able to compare the results from LP0133-1426 with the analyses performed in LP0133-1401 and LP0133-1402 two additional analyses will be performed for the primary endpoint using the supplementary estimand.

THIS DOCUMENT CONTAINS CONFIDENTIAL INFORMATION AND MUST NOT BE COPIED OR MADE AVAILABLE TO ANY THIRD PARTY WITHOUT THE PRIOR WRITTEN CONSENT OF THE LEO PHARMA GROUP

In the primary endpoint additional analysis using the supplementary estimand, observed data including data observed after the occurrence of IE will be used in the analysis, and missing data at Week 16 will be imputed using MI (100 iterations) assuming MAR within treatment group (see [Panel 8](#)). The difference in response rates between the two treatment groups will be analysed using the CMH test stratified by baseline IGA-CHE score. The difference in response rates with 95% CI will be calculated by the Mantel-Haenszel method stratified by baseline IGA-CHE score.

In the sensitivity analysis of primary endpoint additional analysis using the supplementary estimand, observed data including the data observed after the occurrence of IEs will be used in the analysis. Missing data at Week 16 will be imputed as non-response.

The risk difference will be analysed as described above for the analysis of the supplementary estimand. In case of no missing data this analysis will not be performed.

## 5.7 Analysis of pharmacokinetics

The pharmacokinetics analysis is tabulated as described in the CTP Section 14.3.12.

## 5.8 Safety analysis

The analysis of safety will be based on the safety analysis set.

### 5.8.1 Adverse events

AEs will be coded during the course of the trial according to MedDRA version 24.0. AEs will be presented by PTs and primary SOC.

If an AE worsens in severity, the new severity, including date of severity change, will be recorded. If an AE with onset prior to initiation of IMP worsens after administration of IMP, a new AE will be recorded according to CTP Appendix 2. If an AE worsens in severity, the worst severity will be tabulated.

An event will be considered treatment-emergent if started after the first application of IMP or if started before the first application of IMP and worsened in severity after first application of IMP. If an AE started on the same date as the first IMP application, the tick mark from the eCRF indicating if the AE started before the first application of IMP is used to define, if the AE is treatment emergent. The tabulations described in the following will only include the treatment-emergent AEs.

For information about handling of missing data for AEs see the ADRG.

THIS DOCUMENT CONTAINS CONFIDENTIAL INFORMATION AND MUST NOT BE COPIED OR MADE AVAILABLE TO ANY THIRD PARTY WITHOUT THE PRIOR WRITTEN CONSENT OF THE LEO PHARMA GROUP

Treatment-emergent AEs will be summarised; however, all non-treatment emergent AEs will be listed for the SAF and for all screened subjects not in the SAF.

Treatment-related AEs are defined as AEs for which the investigator has described the causal relationship to IMP as possibly or probably related.

An overall summary of AEs, deaths, SAEs, premature discontinuations from IMP and/ or withdrawals from the trial due to AEs, treatment-related AEs, most frequent AEs (5%), severe AEs, outcome of AEs and severity will be presented.

The following AE types will as a minimum be summarized:

- AEs.
- AEs with possible or probable relation to IMP.
- Most frequent AEs ( $\geq 5\%$  in any treatment group).
- SAEs.
- AEs leading to withdrawal from trial.
- AEs leading to permanent discontinuation of IMP.

Evaluation of events will be tabulated by treatment group and be based on the following:

Number of subjects (N), number of subjects with events (n), percent of subjects with events (%), number of events (E), and rate of events per 100 patient years of observation (R).

The overview of AEs will be evaluated as above and will include the following information: seriousness, severity, relatedness, outcome, action taken with IMP, permanent discontinuations from IMP and/or withdrawals from the trial due to AEs.

As a minimum, listings will be provided for:

- AEs.
- SAEs.
- Deaths.
- AEs leading to withdrawal from trial.
- AEs leading to permanent discontinuation of IMP.
- AESIs.
- Other events involving IMP, and AEs originating from other events involving IMP.

The detailed listings will provide an overview of the individual cases and include the age and sex of the participant, whether treatment has been received at the time of AE onset, the AE preferred and reported terms, causality and severity of the AE, the action taken with the IMP, AE outcome, start and stop date of AE, duration of AE, and number of days since first and last IMP administration.

THIS DOCUMENT CONTAINS CONFIDENTIAL INFORMATION AND MUST NOT BE COPIED OR MADE AVAILABLE TO ANY THIRD PARTY WITHOUT THE PRIOR WRITTEN CONSENT OF THE LEO PHARMA GROUP

Narratives will be provided for SAEs and pregnancies.

AESIs will be listed by treatment group. No narratives will be given.

Other events (medication error, misuse, and abuse of IMP) will be tabulated and listed. No narratives will be given.

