THIS DOCUMENT CONTAINS CONFIDENTIAL INFORMATION AND MUST NOT BE COPIED OR MADE AVAILABLE TO ANY THIRD PARTY WITHOUT THE PRIOR WRITTEN CONSENT OF THE LEO PHARMA GROUP

**Abbreviations:** IgE = immunoglobulin E; IL= Interleukin; IMP = investigational medicinal product; JAK = Janus kinase; PDE-4 = phosphodiesterase-4; PUVA = psoralen ultraviolet A; TCS = topical corticosteroids; UVA1 = ultraviolet A1; UVB = ultraviolet B.

As TCS only require 14 days of wash-out prior to baseline, subjects can be instructed to use TCS until 14 days before the baseline visit (Day 1) to alleviate significant worsening of their CHE.

As described in Section 9.5, prohibited medications or procedures used as rescue treatment for intolerable CHE symptoms are allowed, but subjects using rescue treatment must discontinue IMP immediately and will not be allowed to restart treatment with IMP.

All prohibited medications used must be recorded as concomitant medication.

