## 10.3 Early termination assessments

### Permanent discontinuation of IMP

Subjects who permanently discontinue IMP for any reason will be asked to attend an early termination visit as soon as possible after last administration of IMP and return to the trial site for 2 additional visits as indicated below. See the schedule of trial procedures (Section 4) for data to be collected at these visits. The investigator will review any AEs which will be followed up according to Section 13.7, if the subject agrees.

Subjects who permanently discontinue IMP prior to Week 16 will be asked to attend the following visits:

- Early termination visit (as soon as possible after last administration of IMP).
- Safety follow-up visit (2 weeks after last administration of IMP, performed via phone, but can be a site visit if needed).
- Primary endpoint visit (16 weeks after randomisation).

THIS DOCUMENT CONTAINS CONFIDENTIAL INFORMATION AND MUST NOT BE COPIED OR MADE AVAILABLE TO ANY THIRD PARTY WITHOUT THE PRIOR WRITTEN CONSENT OF THE LEO PHARMA GROUP

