### 13.2 Collection of adverse event reports

AE data must be collected from time of first trial-related activity after the subject and/or the parent/guardian has signed the ICF/IAF until subject's completion of the clinical trial (as defined in Section [7.3](#)).

AEs must be assessed by a physician.

At all visits, the subject and/or the parent/guardian will be asked a non-leading question by the investigator about AEs, e.g.: "How have you felt since I saw you last?" No specific symptoms should be asked for, except subject-reported local tolerability which will be queried specifically (see Section [11.5.4](#)) and reported as AE(s) if deemed relevant by the investigator. If the AE qualifies as an SAE, expedited reporting is required (Section [13.4](#)). It is important that the investigator also observes the subject for any changes not reported by the subject and records these changes.

Refer to Sections [11.5.1](#) to [11.5.5](#) for principles for data entry in the eCRF.

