					Difference in mean change (or percentage change)	Efficacy 
 
• Percentage change in HECSI score from baseline to Weeks 4, 8, and 16.
 
 Health-related quality of life and efficacy 
 
• Change in HESD itch score (weekly average) from baseline to Weeks 2, 4, 8, and 16.
 
• Change in HESD pain score (weekly average) from baseline to Weeks 2, 4, 8, and 16.
 
• Change in HESD score (weekly average) from baseline to Weeks 2, 4, 8, and 16.
 
• Change in cDLQI score from baseline to Week 4.
 

- 1) In addition to the secondary safety endpoint listed, clinical laboratory tests, vital signs, and physical examination at screening and end of treatment; use of rescue treatment; and subjects' assessment of local tolerability will be evaluated.
- 2) An event will be considered treatment emergent if started after the first application of IMP or if started before the first application of IMP and worsened in severity after first dose of IMP.
- 3) Among subjects with a baseline HESD itch score (weekly average)  $\geq 4$  points.
- 4) Among subjects with a baseline HESD itch score (weekly average)  $\geq 3$  points.
- 5) Among subjects with a baseline HESD pain score (weekly average)  $\geq 4$  points.
- 6) Among subjects with a baseline HESD pain score (weekly average)  $\geq 3$  points.
- 7) Among subjects with a baseline HESD score (weekly average)  $\geq 4$  points.
- 8) Among subjects with a baseline HESD score (weekly average)  $\geq 3$  points.
- 9) 'Number of treatment-emergent AEs from baseline up to Week 18' will be analysed descriptively according to the specifications in section 5.8.1.

[figure not shown]
**Abbreviations:** AE = adverse event; cDLQI = Children's Dermatology Life Quality Index; CHE = chronic hand eczema; HECSI = Hand Eczema Severity Index; HECSI-75 = at least 75% improvement in HECSI score from baseline; HECSI-90 = at least 90% improvement in HECSI score from baseline; HESD = Hand Eczema Symptom Diary®.

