**5.2 Extent of exposure**

The duration of exposure to treatment will be calculated as the number of days from date of first application of IMP to the date of last application of IMP, both days included.

Exposure to IMP will be presented for the SAF as days of exposure per treatment group. In addition, patient years of exposure and patient years of observation are presented per treatment group. Patient years of exposure will be calculated as the number of days from date of first application of IMP to the date of last application of IMP (both days included) divided by 365.25. Patient years of observation is calculated as number of days from date of randomisation to date of end of trial divided by 365.25.

THIS DOCUMENT CONTAINS CONFIDENTIAL INFORMATION AND MUST NOT BE COPIED OR MADE AVAILABLE TO ANY THIRD PARTY WITHOUT THE PRIOR WRITTEN CONSENT OF THE LEO PHARMA GROUP

In case subjects come in after end of trial (the safety follow-up visit) to e.g., hand in slates or update information on adverse events the time between end of trial and this last contact will not be added to the years of observation.

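### For subjects who stop IMP early, the treatment-emergent AE tables take in off-drug and on-rescue events up to Week 16, and no on-treatment summary separates them

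*SAP*

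**What the plan says.** SAP 5.8.1 classes an AE by its start: "An event will be considered treatment-emergent if started after the first application of IMP", or if it began earlier and then worsened. Protocol 14.3.13.1 has the same rule. Neither mentions the date of last application, and all the AE tabulations that follow in SAP 5.8.1 are restricted to this set.

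There are outer limits. The secondary safety endpoint runs from baseline to Week 18 (Protocol Panel 4, SAP Panel 2), and AEs are collected "until subject's completion of the clinical trial" (Protocol 13.2). Completion means attending both the Week 16 visit and the follow-up visit, whether or not IMP was stopped (Protocol 7.3).

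A subject who stops IMP early has an early termination visit, a safety follow-up 2 weeks after the last application, and a primary endpoint visit at Week 16 (Protocol 10.3). AEs are collected at that Week 16 visit (Protocol Panel 2). Starting rescue treatment ends IMP for good (Protocol 9.5). Under Protocol 9.7, "prohibited medications or procedures used as rescue treatment for intolerable CHE symptoms are allowed". Panel 7 lists systemic corticosteroids and immunosuppressants among the prohibited medications.

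The AE rate in SAP 5.8.1 is per 100 patient years of observation. SAP 5.2 defines the denominator: "Patient years of observation is calculated as number of days from date of randomisation to date of end of trial divided by 365.25". Patient years of exposure are also derived there, but no AE rate uses them. Days since last IMP appear only in the listings.

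**The concern.** One label covers two quite different periods. For a completer, treatment-emergent means on drug plus about two weeks. For an early stopper, it can mean a few weeks on drug followed by up to three months off drug, perhaps on a systemic or potent topical rescue medication. Clinically significant worsening of the eczema is itself reportable as an AE (Protocol 13.6.4), so deterioration after IMP stops enters the same tables.

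The protocol says that rescue and discontinuation are most often due to lack of efficacy or to treatment features the subject finds unacceptable (Protocol 5.3). If the drug works, the two groups may well stop at different rates and so contribute different amounts of off-drug time. A reader of the AE tables would take the percentages and rates as a picture of events on delgocitinib and on vehicle. No planned table would show whether a difference arose on treatment or after it. The vehicle group has only 23 subjects, so a few late events could show.

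**Working it through.** **The plan's own dates.** Baseline is Day 1. Week 16 is 1 + 16 × 7 = Day 113, and follow-up two weeks later is 113 + 14 = Day 127. Both agree with Protocol Panel 2.

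**Completer.** Exposure, counting both end days, is 113 days. Observation is 127 − 1 = 126 days. Off-drug time is 126 − 113 = 13 days (14 if calendar days 114 to 127 are counted), or 13/126 = 10.3%. All of it lies within last IMP + 14 days.

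**Early stopper who returns at Week 16.** Observation is 113 − 1 = 112 days. With last IMP on Day L, off-drug days are 112 − L, and days beyond last IMP + 14 are 98 − L.

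| Last IMP | Off-drug days observed | Of these, beyond last IMP + 14 |
|---|---|---|
| Day 14 | 98 | 84 |
| Day 28 | 84 | 70 |
| Day 56 | 56 | 42 |
| Day 84 | 28 | 14 |

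This takes end of trial as the subject's last visit, as in Protocol 11.9. A bracketed remark in SAP 5.2 equates it with the safety follow-up visit, which for most early stoppers comes before Week 16. On that reading the denominator would stop before AE collection does.

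**Share of a group's observation time beyond last IMP + 14 days.** Let f be the proportion stopping early. The documents give no figure, so f is assumed to be 5% to 30%:

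s = f(98 − L) / [126(1 − f) + 112f]

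For example, f = 20% and L = 28 gives 0.2 × 70 / (100.8 + 22.4) = 14/123.2 = 11.4%.

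| f (assumed) | L = 28 | L = 56 |
|---|---|---|
| 5% | 2.8% | 1.7% |
| 10% | 5.6% | 3.4% |
| 20% | 11.4% | 6.8% |
| 30% | 17.2% | 10.3% |

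**Effect on rates.** Let q be the event rate beyond the window divided by the rate within it. The reported rate divided by the in-window rate is 1 + s(q − 1). Take L = 42 in both groups (assumed). Then s is 2.8/125.3 = 2.2% at f = 5%, 11.2/123.2 = 9.1% at f = 20%, and 16.8/121.8 = 13.8% at f = 30%. The delgocitinib-to-vehicle rate ratio is multiplied by:

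| Stopping, delgocitinib vs vehicle (assumed) | q = 0 | q = 1 | q = 1.5 |
|---|---|---|---|
| 5% vs 20% | 1.075 | 1.000 | 0.967 |
| 5% vs 30% | 1.134 | 1.000 | 0.946 |

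**Effect on incidence.** Percentages count subjects. One additional vehicle subject adds 1/23 = 4.3 points and one additional delgocitinib subject adds 1/69 = 1.4 points. This happens only if that subject had no earlier event in the row being counted. Compared with an on-treatment count, late events can raise an incidence but not lower it.

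**The case against.** Full follow-up is a defensible, inclusive choice in adolescents given a JAK inhibitor, and narrowing the main tables would take late-onset events out of view. The safety objective is to evaluate delgocitinib and does not name a comparison with vehicle. The endpoint is descriptive and no test rests on it. Events judged possibly or probably related have their own table. The listings show whether treatment had been received at onset and the days since last IMP, and rescue treatment is tabulated and plotted. With 92 subjects and a low discontinuation rate anticipated (Protocol 14.3.5.1), late events could be reviewed case by case. Subjects who decline the Week 16 visit are withdrawn (Protocol 10.1) and would add no late events.

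Most of this stands, and it is why the main tables should not change. Replacing them would also displace the protocol's baseline-to-Week-18 endpoint. But the related-AE table depends on event-by-event causality judgement, and listings give neither an incidence nor a rate. The plan has no summary limited to the treatment period.

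A reader might infer that post-rescue events load onto vehicle and hide an excess on delgocitinib, while off-drug time dilutes the rates. The documents do not support that. Provided that end of trial is the last visit, numerator and denominator cover the same period, so a rate falls only if events are less frequent off drug (q below 1). If vehicle subjects stop more often, dilution would lower the vehicle rate, which works against masking.

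**Conclusion.** The point holds in limited form. What is missing is a limit tied to last IMP. It would be wrong to say that collection is open-ended, because Week 18 and trial completion bound it. It would also be wrong to say that events are charged to the randomised arm, because the safety set follows treatment actually received (SAP Panel 5).

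The calendar result needs only that the early stopper returns at Week 16: 70 days beyond the 2-week follow-up for last IMP on Day 28, against none for a completer. The group-level sizes rest on assumed stopping proportions and dates. They run from 1.7% to 17.2% of observation time, with a rate-ratio factor from 0.946 to 1.134 in the scenarios tried. With discontinuation as low as the protocol expects, the effect would be towards the small end. The direction for rates cannot be known in advance. This is a worthwhile, inexpensive improvement to descriptive safety reporting and does not affect any confirmatory conclusion.

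**What to change.** Keep the protocol-defined baseline-to-Week-18 treatment-emergent tables as the main AE tables. Before unblinding, add to SAP 5.8.1:

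- a supplementary on-treatment AE summary by treatment received, with onset from first IMP to last IMP + 14 days (the protocol's own follow-up interval) and person-time cut at the same point;
- a flag, in the tables or listings, for AEs with onset after initiation of rescue treatment.

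The inputs are already collected: AE start dates (Protocol 13.3), the date of last IMP (Protocol 11.9) and the rescue start date (SAP 5.3). Completers' results will be essentially the same in both sets. The cost is one extra set of AE tables.
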